# 3.2.13.13 Time to Retreatment

Time to retreatment in weeks will be calculated as ((Date of Retreatment - injection date) + 1) / 7.

Subjects who are never retreated will be censored at their last recorded visit for the study.

### 3.2.13.14 Concomitant Therapy Duration

If times are available, the duration of concomitant treatments/physiotherapy etc. will be calculated as (end date/time - start date/time). If at least one time is missing, the duration of concomitant treatments will be calculated as (end date - start date) +1. If the recorded end date is CONT. (for continuing) then the end date will be listed as "ongoing" and the duration will be approximated as " $\geq$ (last attended visit date start date)+1" day(s). If the start date or the end date are partial, the duration will be presented as an inequality " $\geq$ xx" day(s) (i.e.:  $\geq$ 2 where start date 31JAN2004 and end date=FEB2004 or start date=JAN2004 and end date=01FEB2004) but if both are partial or one is missing the duration will not be presented.

### 3.2.13.15 Study Day

Study day will be defined as '-1' for the day prior to first study drug administration and as '1' for the day of first study drug administration (i.e. day 0 does not exist). If an event/assessment date was on or after first study drug administration then

Study day = event/assessment date was before first study drug administration date + 1 If an event/assessment date was before first study drug administration then

Study day = event/assessment start date study drug administration then table = table

### *3.2.13.16 Treatment Cycle Day*

If an event/assessment takes place/starts during Treatment Cycle X then the associated Treatment Cycle X day will be defined as:

Treatment Cycle X day = (event/assessment start date Treatment Cycle X study drug administration date) + 1

For any Treatment Cycle, the Treatment Cycle day is defined as '1' for the day of study drug administration (i.e. day 0 does not exist).

The Treatment Cycle corresponding to the Treatment Cycle day will also be identified as follows and will be displayed jointly with the Treatment Cycle day in the listings:

- For Treatment Cycle 1: T1
- For Treatment Cycle 2: T2
- For Treatment Cycle 3: T3
- For Treatment Cycle 4: T4

### 3.2.13.17 Botulinum Toxin Treatment Duration

The duration of BTX treatments will be calculated as (end date - start date) +1. If the start date or the end date are partial, the duration will be presented as an inequality " $\geq xx$ " day(s) (i.e.:  $\geq 2$  where start date 31JAN2004 and end date=FEB2004 or start date=JAN2004 and end date=01FEB2004) but if both are partial or one is missing the duration will not be presented.

### 3.2.13.18 Centre Post Pooling

For definition see section 3.2.16.

3.2.13.19 Modified Ashworth Scale

In order to perform the quantitative analyses on the MAS score, the original score '1+' will be considered as the derived numeric score '2' and the higher original numeric scores will be incremented by one.

The below table summarises the correspondences between the original MAS scores and the derived MAS scores.

| Original MAS score | Derived MAS score |
|--------------------|-------------------|
| 0                  | 0                 |
| 1                  | 1                 |
| 1+                 | 2                 |
| 2                  | 3                 |
| 3                  | 4                 |
| 4                  | 5                 |

 Table 9
 Correspondence between Original MAS Scores and Derived MAS Scores

### 3.2.13.20 Goal Attainment Scale

The GAS score is calculated as:

$$50 + \frac{10\sum_{i=1}^{n} w_i x_i}{\sqrt{0.7\sum_{i=1}^{n} w_i^2 + 0.3(\sum_{i=1}^{n} w_i)^2}}$$

Where:

- xi = the rating of the ith goal post-baseline (-2: Much less than expected outcome, -1: somewhat less than expected outcome, 0: expected outcome, 1: somewhat more than expected outcome, 2: Much more than expected outcome)
- wi = the weight of the ith goal, calculated as importance \* difficulty as defined at baseline.

- Importance 0: not at all important, 1: a little important, 2: moderately important, 3: very important
- Difficulty 0: not at all difficult, 1: a little difficult, 2: moderately difficult, 3: very difficult
- n = the number of goals assessed at baseline and post-baseline [5,6]

# 3.2.13.21 Pediatric Quality of Life InventoryTM

Each generic core scale (total scale score, physical health summary score and psychosocial health summary score) and each cerebral palsy specific score (Daily Activities, School Activities, Movement and Balance, Pain and Hurt, Fatigue, Eating Activities, and Speech and Communication) is calculated as follows:

(1) Individual item scores are reversed and transformed from a 0-4 scale to a 0-100 scale by assigning 0=100, 1=75, 2=50, 3=25 and 4=0

(2) Each scale score is calculated as the sum of the transformed individual item scores, divided by the number of non-missing items

Note that a scale score is only calculated if at least 50% of the associated items are non-missing.

The items for each cerebral palsy specific score are identified on the eCRF. The generic core scales comprise the following sections:

- Physical health summary scale: Physical functioning scale
- Psychosocial health summary scale: Emotional, social and school functioning scales
- Total Scale: All scales [14, 15].

## 3.2.13.22 Electrocardiogram Average Result

For each quantitative ECG parameter the average result at each visit will be calculated as follows:

Average ECG result = sum of non-missing results at that visit / number of non-missing results at that visit.

3.2.13.23 Type of ECG Abnormality "Other Conduction Abnormalities"

That will gather all types of conduction abnormalities other than Left bundle branch block, Right bundle branch block, 2nd and 3rd degree AV block.

## 3.2.13.24 Class of ECG Abnormality "Other Abnormalities"

That will gather all abnormalities not categorized as MI, arrhythmia, ST abnormalities, T-wave abnormalities and U-wave abnormalities.

## 3.2.13.25 New Morphologies

New morphologies will include all morphology abnormalities occurring after baseline that were not present at baseline.

## 3.2.13.26 Special Interest Flag for AE

An AE of special interest is defined as described in section 3.2.3.1.

## 3.2.14 Visit Windows

All data will be organised and analysed according to the scheduled visits outlined in the protocol. However, if more than one record occurs within the same time interval where only one assessment is expected then the following rule should be applied: for pre-treatment assessments the last non-missing reliable result prior to study drug

administration will be used; for week 2 assessments, the closest non-missing reliable result to the scheduled visit will be used; for post-treatment assessments the closest non-missing reliable result to the scheduled visit will be used. An assessment will be considered reliable if it is performed without any technical problem and if the result is within the range of plausible values.

| Study period   | Scheduled visit             | Visit Window (days)           |  |  |
|----------------|-----------------------------|-------------------------------|--|--|
|                |                             |                               |  |  |
| Pre treatment  | Screening                   | -7 to 1                       |  |  |
|                |                             |                               |  |  |
| Treatment      | Baseline                    | 1 (prior to first dose)       |  |  |
| Cycle 1        | Week 2 (Telephone contact)  | 8 to 22                       |  |  |
|                | Week 4 (Telephone contact)  | 22 to 36                      |  |  |
|                | Week 6                      | 39 to 47                      |  |  |
|                | Week 12                     | 78 to 92                      |  |  |
|                | Week 16 (Telephone contact) | 99 to 127                     |  |  |
|                | Additional visits           | Every 42 days (± 7 days)      |  |  |
| [              |                             |                               |  |  |
| Treatment      | Day 1                       | Treatment Cycle Day 1         |  |  |
| Cycles 2, 3, 4 | Week 2 (Telephone contact)  | Treatment Cycle Day 8 to 22   |  |  |
|                | Week 4 (Telephone contact)  | Treatment Cycle Day 22 to 36  |  |  |
|                | Week 6                      | Treatment Cycle Day 39 to 47  |  |  |
|                | Week 12                     | Treatment Cycle Day 78 to 92  |  |  |
|                | Week 16 (Telephone contact) | Treatment Cycle Day 99 to 127 |  |  |
|                | Additional visits           | Every 42 days (± 7 days)      |  |  |

#### Table 10 Visit windows

### 3.2.15 Rules and Data Formats

Data will be presented using an appropriate number of decimal places (i.e. the number of decimal places used does not imply undue precision). Raw data will be presented to the number of decimal places collected and derived data will be presented to an appropriate number of decimal places. The appropriate number of decimal places will be determined by general practice, mathematical rationale or scientific rationale (e.g. age should be presented in whole numbers).

Descriptive statistics will include n, n missing, and:

- Mean, standard deviation, minimum, median, maximum and 95% CI for means for interval-type variables
- Counts and percents of each category for categorical nominal variables
- Both for categorical ordinal variables.

Mean, median, standard deviation and standard errors of the mean values will be reported to one decimal place greater than the raw/derived data that they summarise. Minimum and maximum values will be reported with the same precision as the raw data. Lower and upper CI values will be presented to one decimal place more than the raw/derived data (i.e. to the same number of decimal places as the mean). Percentages will be reported to one decimal place and 0% will not be presented. Percentages will be calculated using a denominator of all subjects in a specified population. The denominator will be specified in a footnote to the tables for clarification if necessary.

All values below or above a limit of detection (e.g. <0.1 or >100) will be listed as such. These values will not be included in any summary statistics.

All text fields must be left justified and numeric or numeric with some text specification (e.g. not done, unknown, <4.5, ...) must be decimal justified. Dates will be presented in the format ddMMMyyyy and times in the format hh:mm.

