Electrocardiogram test results will be recorded by the central laboratory and provided to the study Sponsor, and to the study sites for evaluation of clinically significant changes. See Section 10.1.7 for recording clinically significant abnormal ECG findings that should be recorded as AEs in the eCRF.

8.2.5 *Clinical Laboratory Tests*

Blood samples for clinical chemistry (including serum ALP - total and bone isoenzyme, and HbA1c) will be collected at Treatment 1, Day 1 (baseline) and at the end of study visit or early withdrawal. In addition, a blood sample for serum ALP - total and bone isoenzyme, and HbA1c only will be collected at Treatment 1, Week 16. Absolute values and change from Baseline will be analysed.

The following will be assessed:

Clinical Chemistry (3.5 mL blood): urea, creatinine, total bilirubin, conjugated bilirubin, chloride, bicarbonate, sodium, potassium, calcium, phosphate, serum ALP - total and bone isoenzyme, aspartate aminotransferase, alanine aminotransferase, gamma-glutamyl transferase, albumin, total protein, total cholesterol, triglycerides and HbA1c.

Pregnancy: At Day 1 of each treatment, the Tanner Grading Scale for breast development will be performed for all female subjects (further details are provided in Appendix 8) [54]. For all female subjects of childbearing potential and for those subjects reaching Tanner Stage II or more breast development, a urine sample will be collected for a pregnancy test. The test will be performed on site using a urine pregnancy test provided by the Sponsor.

If it is anticipated that urine collection may not be possible on site, parents will be instructed to collect a urine sample (at least 15 mL) at home in a clean dry vial on the day preceding the visit. The urine sample will be stored in the fridge (between 2°C and 8°C). Parents will take the urine sample to the investigational site where the test will be performed.

If the urine pregnancy test is found to be positive, it will be followed up with a serum pregnancy test (1 mL blood) conducted at the central laboratory.

Clinical laboratory tests will be performed by a central laboratory. Details of the methodology and reference ranges will be provided in the Trial Master File.

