11.4.4 Safety Evaluation

The safety endpoints of the study are:

- Treatment emergent adverse events.
- Vital signs (systolic and diastolic BP and HR): absolute values and change from Baseline at each visit to the study centre.
- Body weight and height: absolute values and change from baseline at Week 16 of each treatment and at the end of study visit or early withdrawal.
- Clinical chemistry (including serum ALP - total and bone isoenzyme, and glycosylated HbA1c): absolute values and change from Baseline at Treatment 1, Week 16 (serum ALP - total and bone isoenzyme, and HbA1c only) and at the end of study visit or early withdrawal.
- Presence of BTX-A-Abs at baseline and at the end of study visit or early withdrawal.
- A 12-lead ECG: absolute values and change from Baseline in ECG parameters and morphology at Treatment 1, Week 6 and at the end of study visit or early withdrawal.

All safety data will be included in the safety data listings and summary tables will be produced on the safety population. Descriptive statistics will be provided for the safety endpoints.

Adverse Events

Adverse events will be coded using the Medical Dictionary for Regulatory Activities (MedDRA, version in force at the time of database freeze).

All AEs reported during the study will be presented in a listing which will be sorted by treatment group, subject ID, primary system organ class (SOC), preferred term, verbatim text and start date.

Listings of all SAEs, AEs leading to withdrawal and deaths reported during the study will also be presented by treatment group and subject ID.

A TEAE is defined as any AE that occurs during the treatment phase of this study if:

- (1) It was not present prior to the first of intake of study treatment, or
- (2) It was present prior to the first intake of study treatment but the intensity increases during the treatment phase of this study.
- (3) It was present prior to receiving the first dose of study treatment, the intensity is the same but the drug relationship became related during the active phase of the study.

An overall summary table of all AEs will be presented. In summaries of intensity, causality, and causality combined with intensity, subjects may be reported in more than one category in these tables according to how many different levels of intensity and causality are associated to the AEs they experience.

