## 3.2.3.3 Laboratory Data

For clinical laboratory safety tests (clinical chemistry including serum alkaline phosphatase total and bone isoenzyme, and HbA1c), all data will be listed, in standard international (SI) units, by subject ID and assessment visit, and all abnormal values will be flagged (High [H], Low [L], or clinically significant [C]).

A listing will be presented of all values for a subject with at least a clinically significant abnormal value.

A separate listing of normal ranges for SI units will be provided by gender and age where relevant.

Baseline will be defined as the last measurement collected prior to receiving the initial study treatment, Treatment Cycle 1 on Day 1. For the fixed dose Treatment Cycle 1 Baseline and Week 16 will be presented by Study Limb Dose. For Repeat Treatment Baseline and EOS/EW will be presented by Total Body Dose and subjects will be assigned to the treatment group according to the last study treatment received.

Summary statistics for all laboratory parameters by treatment group will be presented at each scheduled assessment (Baseline, Treatment Cycle 1 Week 16, and EOS/EW) for actual values and changes from baseline. The number and percentage of subjects with low, normal or high values will also be presented, for each treatment group, at each scheduled assessment. In addition, shift from Baseline tables of the number and percentage of subjects with low, normal or high values will or high values will be presented for each treatment group, at each scheduled assessment, and an overall summary of shift from baseline throughout the study will also be provided.

Results from urine and serum pregnancy tests will be listed by subject ID and assessment visit.

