## 3.2.13.4 Changes from Baseline

Changes from baseline to any visit will be calculated as a difference from baseline (e.g. assessment at the visit assessment at baseline).

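### Results beyond a detection limit are left out of all summary statistics, so descriptive laboratory tables move away from the censored tail and cannot show the extreme value

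*SAP*

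**What the plan says.** SAP 3.2.15 sets the rule in two sentences: "All values below or above a limit of detection (e.g. <0.1 or >100) will be listed as such", and then "These values will not be included in any summary statistics". It covers both tails and is not restricted to one data type. Among the data this trial plans to collect, it bears mainly on clinical chemistry.

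The same section defines the statistics concerned: "Mean, standard deviation, minimum, median, maximum and 95% CI for means for interval-type variables".

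SAP 3.2.3.3 (Laboratory Data) applies them: "Summary statistics for all laboratory parameters by treatment group will be presented at each scheduled assessment", for actual values and changes from baseline. It then adds categories: "The number and percentage of subjects with low, normal or high values will also be presented", followed by shift tables. It also lists all data, flags abnormal values as high, low or clinically significant, and gives a separate listing for subjects with a clinically significant abnormal value.

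Under SAP 3.2.13.4, "Changes from baseline to any visit will be calculated as a difference from baseline", so both values must be numeric. Protocol 8.2.5 (Clinical Laboratory Tests) says of the chemistry data: "Absolute values and change from Baseline will be analysed". Protocol 11.4.4 makes the safety analysis descriptive: "Descriptive statistics will be provided for the safety endpoints".

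The missing-data section (SAP 3.2.4.1) covers efficacy imputation, retests, missing intensity or causality of adverse events, and case-by-case decisions before unblinding. Nowhere do the documents provide a substitution, a censored-data method or a count of the excluded results.

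**The concern.** A result reported as greater than a limit is not missing. Its exact value is unknown, but it is known to be extreme. Leaving it out is informative exclusion, because whether a result stays in the table depends on the result itself.

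Two consequences need no assumption about frequency. First, the minimum and maximum are required statistics, and under this rule neither can be a result beyond a limit, even if only one subject has one. The table then shows a less extreme value as the worst observed. Second, no count of what was removed is required. The SAP does not say whether these results enter the number missing.

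The SAP treats partial information differently elsewhere. Durations based on partial dates are kept as inequalities (3.2.4.2, 3.2.13.5), and subjects never retreated are censored rather than deleted (3.2.13.13).

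At stake is how faithfully the laboratory tables describe the data, in a trial whose secondary objective is long-term safety.

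**Working it through.** The documents state no figure to reproduce. The share f of results beyond a limit, the distribution and the correlation between visits are all assumptions.

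**1. Mean of a lognormal analyte.** Let X = exp(sZ) with Z standard normal, c = Φ⁻¹(f) and u = Φ⁻¹(1−f). Ratios to the true mean exp(s²/2):

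- lowest share dropped: Φ(s−c)/(1−f)
- lowest share set to the limit: Φ(s−c) + f·exp(sc − s²/2)
- highest share dropped: Φ(u−s)/(1−f)
- highest share set to the limit: Φ(u−s) + f·exp(su − s²/2)

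Example with f = 10% and s = 0.5, so c = −1.2816 and u = 1.2816:

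- lower tail dropped: Φ(1.7816)/0.9 = 0.9626/0.9 = 1.070
- lower tail set to the limit: 0.9626 + 0.1 × 0.4650 = 1.009
- upper tail dropped: Φ(0.7816)/0.9 = 0.7827/0.9 = 0.870
- upper tail set to the limit: 0.7827 + 0.1 × 1.6750 = 0.950

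Error in the mean over s = 0.3, 0.5, 0.8 and 1.0:

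| Share censored | Lowest dropped | Lowest set to limit | Highest dropped | Highest set to limit |
|---|---|---|---|---|
| 1% | +0.6 to +1.0% | below +0.1% | −1.2 to −8.3% | −0.2 to −3.0% |
| 10% | +4.8 to +9.9% | +0.6 to +0.9% | −7.0 to −32.1% | −2.3 to −17.1% |
| 30% | +13.6 to +33.8% | +4.0 to +5.1% | −15.9 to −54.7% | −7.6 to −37.5% |

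**2. Median and SD, standard normal analyte, one tail dropped.** The mean shift is φ(c)/(1−f); at f = 10% this is 0.1755/0.9 = 0.195 SD. The median shift is Φ⁻¹(f + (1−f)/2). For f = 1% / 5% / 10%:

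- the mean moves by 0.03 / 0.11 / 0.20 SD
- the median moves by 0.01 / 0.06 / 0.13 SD
- the SD falls to 0.97 / 0.90 / 0.84 of its true value

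If equal shares are dropped from both tails, mean and median do not move. The SD still falls, to 0.87 / 0.79 at a total of 5% / 10%. Setting to the limit keeps the order of the values, so the median is unchanged while fewer than half are censored in one tail.

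**3. Change from baseline.** This was simulated with 2,000,000 bivariate normal pairs. The lower limit cuts off 5% / 10% / 20% of baselines, and a pair is lost if either value is below it.

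| True mean change | Reported, correlation 0.5 | Reported, correlation 0.7 |
|---|---|---|
| −0.5 SD | −0.43 / −0.40 / −0.35 | −0.46 / −0.43 / −0.40 |
| +0.5 SD | 0.47 / 0.44 / 0.40 | 0.48 / 0.46 / 0.44 |
| 0 | 0 | 0 |

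For a true change of −0.5 SD, 14% to 44% of pairs are lost. A true non-zero change is pulled towards zero; a true zero change stays zero.

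**The case against.** The strongest reply is that little is lost in practice. All laboratory data are listed and abnormal values are flagged. SAP 3.2.3.3 introduces the low/normal/high counts as an addition to the summary statistics, so the exclusion most naturally applies to the numeric statistics alone. Protocol 8.2.5 has clinically relevant abnormal tests repeated, and Protocol 10.1.5 has clinically significant abnormalities reported as adverse events. No assay limit is given, and no analyte is named for which a large share would be censored. At 1% in the lower tail the effect on the mean is at most 1%.

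Most of this stands, and it rules out three stronger readings.

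- A reader might infer that a rise above an upper limit disappears from the safety report. It does not: it stays in the flagged listings and, on the natural reading, in the category and shift tables.
- A reader might infer a bias in one fixed direction, towards the centre. The direction depends on which tail is censored, and balanced censoring of a symmetric distribution moves neither mean nor median.
- A reader might infer that substituting the limit removes the problem. In the table above that is nearly true for the lower tail but not for the upper.

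The reply does not restore the minimum and maximum, the lost change pairs or the missing count. It also leaves the scope of the exclusion to inference, because the SAP does not say whether the category and shift tables fall under it.

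**Conclusion.** The point holds as a defect in the descriptive laboratory summaries. The rule is explicit and nothing in the documents softens it. Followed as written, it moves means and medians away from the censored tail, shrinks the SD, hides the extreme minimum or maximum and discards change-from-baseline pairs.

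The size cannot be fixed from the documents. It is negligible for a lower tail with 1% censored, and it is substantial for a skewed analyte with 10% censored in the upper tail. These magnitudes rest on the assumed lognormal or normal models and assumed shares; the loss of the extreme value and of the pairs does not.

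The concern does not extend to efficacy. MAS and PGA are bounded scales and GAS is a derived score, so the primary and secondary endpoints, alpha and power are unaffected.

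**What to change.** Replace the exclusion sentence in SAP 3.2.15, before unblinding, with wording such as:

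*A result reported only as less than or greater than a detection limit will be set to that limit for summary statistics and changes from baseline. It will be classified in the low/normal/high and shift tables. The number of such results will be shown for each parameter, visit and treatment group. A minimum or maximum that is such a result will be displayed with its < or > sign.*

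The cost is a short SAP edit, a simple derivation and one extra count in the laboratory tables. The downside is residual substitution error. Under the lognormal assumption it is about 0–5% of the mean for lower-limit values with up to 30% censored. For upper-limit values it is 0.2–3% at 1% censored and 2–17% at 10%. The displayed count lets a reader see where that error could matter.
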